the spouse/partner about the survey opportunity. We will also ask participating employees/supervisors to invite their spouses/partners to participate in this study after they complete the baseline survey and/or when we distribute the actigraphy watches in person. We will also post spouse-specific recruitment flyers, postcards and FAQs on-site during our visit to ORNG locations. After participating employees/supervisors complete the first survey, and after we receive the contact information (names and email addresses) of spouses/partners who express interest in participating in this study, we will send the spouses an email inviting them to sign up for the study and begin the first baseline survey. We will also have a phone number and email for spouses (and employees or supervisors) to reach out with any questions regarding the study.

Of the 500 employees we will recruit, we anticipate that approximately 80% (400) of the employees will be married, engaged, and/or cohabiting, based on our prior work. Similarly, we have previously obtained response rates of about 50-65% for spouses and therefore, we expect that approximately 65% of those spouse/partners will agree to participate in the study (i.e., 260). We anticipate an 80% response rate at the 4-month and 9-month follow up for spouses (N=208 and N=166, respectively).

We will use incentives to aid recruitment of supervisors, employees, and spouse/partners. While we anticipate training supervisors during company time, we have found in our past organizational research experience that providing participant payment helps to increase participation. Thus, we plan on providing supervisors and employees a \$50 incentive for completing a survey and wearing the actigraph watch during baseline and during 9-month post-baseline, and a \$25 incentive for completing a survey at 4-month post-baseline – thus they can earn up to \$125 total (\$50 baseline, \$25 4-month post-baseline, and \$50 9-month post-baseline). Employees' spouses/partners will be invited to complete three \$25 surveys for baseline, 4-month post-baseline, and 9-month post-baseline, thus potentially earning up to \$75 total. These monetary incentives will be provided in ClinCards, which are reloadable debit cards, and they will be given to the participants subsequent to the completion of each time point (baseline, 4-month post-baseline and 9-month post-baseline). We will also provide food and beverages during on-site recruitment.

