We plan on taking a cluster, or group, randomization approach, or more specifically, a sequential cluster random assignment within Blocks (see Table below) to assign participants to treatment and control conditions. Based on the list of locations and units, we will identify approximately 24 clusters for the study, half to be randomized to the intervention group and half to control. Randomization will occur once units have been identified and before data collection. The research team recruiting and collecting data will be kept blind of the randomization results.

Further clustering of facilities into groups of facilities is a second level of clustering. There are several reasons for this extra step. First, clustering facilities that are geographically close will help to minimize research-related travel expenses to the facilities because travel to several facilities in the same study intervention arm can be accomplished in one trip. Second, clustering facilities that are geographically close will help to minimize contamination across study intervention arms as geographically close facilities will tend to be assigned to the same intervention condition; furthermore, this may also serve to boost intervention effects as supervisors in intervention locations that are geographically close may talk with one another and share ideas and experiences. Third, creating clusters of facilities will help to balance better the number of employees across the study intervention conditions, an important issue given the variability in employees in facilities across the state.

Based on our recruitment projections (500 employees, 200 supervisors), the table below breaks down the randomization numbers. Within each of 3 Blocks, there will be 8 total clusters, randomized into 4 treatment and 4 control. The cluster of 4 represents the second layer described in the paragraph above. Based on a preliminary roll out plan, we anticipate that Block 2 will be slightly larger than Blocks 1 and 3.

Randomization Design Plan

	Intervention	Control
Block 1 (begins Year 1)	4 clusters of units 
 ~ 75 employees across units (non-supervisor) ~ 30 supervisors 	4 clusters of units 
 ~ 75 employees across units (non-supervisor) ~ 30 supervisors

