This section documents the power analyses we conducted for the planned analyses for hypothesis testing. We focus on power for the analyses involving employee-level outcomes. To estimate power for Service member-level outcomes, we based our effect size estimate for the intervention's effect on physical health from the data reported in Hammer et al. (2011), i.e., $d = .33$ ($ICC = .03$) after controlling for baseline physical health and a workplace intervention's effect on sleep problems ($d = .30$; $ICC = .01$) from (Adler, Gunia, Bliese, Kim & LoPresti, working paper). We assumed 24 randomized clusters. Throughout, we set alpha = .05 to define statistical significance. Power analyses for the employee-level outcomes were conducted using Optimal Design (Version 2.01) software package (Raudenbush, Spybrook, Congdon, Liu, and Martinez, 2011). With these assumptions, the estimated power for the effect of the intervention on physical health would be .95 and on sleep problems would be .83 with 500 enrolled employees at baseline. Assuming an attrition rate of 20% (see Missing Data discussion below) resulting in a total sample size of 400 employees across the 24 randomized clusters, the estimated power for the effect of the intervention on physical health would be .86 and on sleep quality would be .80. Thus, we have demonstrated adequate power to test our hypotheses for employees.

Missing Data and the Application of Intent-to-Treat:

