Missing data intermittently during the study and/or dropouts are inevitable and an issue faced by all longitudinal studies. There is no consensus, however, on the optimal analytical strategy to analyze missing data. Using the standard missing data taxonomy (Rubin, 1987), we will follow the recommendations made by Nich and Carroll (1997, 2002) and conduct intent-to-treat analyses using three strategies. In the first strategy we will extend the multiple imputation method of Little and Yau (1996) to allow for non-monotone missing values, which could occur intermittently during the study period. Monotone missing patterns require subsequent variables to be missing once a variable is missing. We will impute unobserved outcomes based on study condition, observed subject-level covariates at baseline and observed follow-ups. Inferences will be made on imputed datasets using Rubin's method (Barnes, Lindborg, & Seaman, 2006; Rubin, 1996). Our second analytical strategy will consider selection models and pattern-mixture models (Michiels, Molenberghs, Bijnens, Vangeneugden, & Thijs, 2002) based on different factorization of the joint distribution of the response variables and the missing patterns. As different strategies require different assumptions for the estimated treatment effects to be unbiased and some assumptions are not testable, comparisons of these strategies serve mainly as sensitivity analyses of their influence on the estimated key parameters of each Aim. A third strategy will consider the use of Full Information Maximum Likelihood methods in the analysis of incomplete data as implemented in several software programs (e.g., Mplus; Muthén & Muthén, 2007). As mentioned in the prior section, this study is adequately powered for an attrition rate of 20%.

Analysis of Research Questions/Hypotheses:

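### The statement that the study is adequately powered at 20% attrition rests on an employee-only calculation; spouse and supervisor outcomes, also under the primary hypotheses, have no power figure and fall well short on the employee inputs

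*Combined protocol and SAP*

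**What the plan says.** Section (8), Power Analysis, confines itself to employee-level outcomes and concludes that power is adequate for employees. It reports power of .95 (physical health) and .83 (sleep problems) for 500 employees. Then, "Assuming an attrition rate of 20% (see Missing Data discussion below"), it reports .86 and .80 for 400. The next subsection, on missing data, refers back to that result but words it for the whole trial: "this study is adequately powered for an attrition rate of 20" percent. Each subsection points to the other for the 20%, and neither gives a source.

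Section (2), Objectives, lists under its primary hypotheses and research questions the supervisors' sleep, health and injury, the spouses' family processes and health, and workplace outcomes for all three groups.

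Section (5), Recruitment Methods, gives the spouse numbers. Of 500 employees, 80% (400) are expected to have a partner. On uptake: "we have previously obtained response rates of about 50-65% for spouses and therefore, we expect that approximately 65" percent will take part, which is 260. On follow-up: "We anticipate an 80% response rate at the 4-month and 9-month follow up for spouses (N=208 and N=166, respectively"). Section (5) expects 200 supervisors and gives no retention figure for them.

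**The concern.** The sentence covers more than the calculation behind it. A reader who takes it at its word will suppose that every primary hypothesis was sized, including those on spouses and supervisors, although those groups are far smaller than the 500 employees. If the wording passes into reports, a non-significant spouse or supervisor result could appear better supported than it is. The reader also has no stated detectable effect against which to judge it.

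**Working it through.** **Inputs.** Clusters: "We assumed 24 randomized clusters". Allocation: "half to be randomized to the intervention group and half to control", so 12 against 12. Significance: "we set alpha = .05 to define statistical significance"; sidedness is not stated and two-sided is assumed. Employee inputs from Power Analysis: d=.33 with ICC .03 (physical health, after baseline adjustment) and d=.30 with ICC .01 (sleep). The plan does not define adequate power; the lowest value it accepts is .80.

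**Formula.** For J=24 clusters, N people and m=N/24, the noncentrality is λ = √{J·d² / [4(ICC + (1−ICC)/m)]}. Power comes from the noncentral t with J−2=22 df (critical value 2.074).

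**The plan's own figures first.**
- Physical health, N=500: m=20.83, λ=√(2.6136/0.3062)=2.92, power .80 (stated .95).
- Physical health, N=400: m=16.67, λ=√(2.6136/0.3528)=2.72, power .74 (stated .86).
- Sleep, N=500: λ=3.06, power .83 (stated .83).
- Sleep, N=400: λ=√(2.16/0.2776)=2.79, power .76 (stated .80; a normal approximation gives .797).

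Only the sleep figure at 500 reproduces by this method. No single variant tried (normal approximation, one-sided test, zero ICC, other df, cluster-level covariates, swapped inputs, 48 clusters, supervisors added to N) gives all four. The physical-health pair also does not fit together. Falling from .95 to .86 needs λ² to drop by a factor of about 1.41, or 1.35 with rounding in the pair's favour. Going from 500 to 400 people in 24 clusters can change λ² by at most 500/400=1.25, whatever the ICC.

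**Spouse numbers.** 500×.80=400. At 65% uptake: 400×.65=260; 260×.8=208; 208×.8=166.4. Retention at 9 months is .8×.8=.64, a 36% loss. At 50% uptake: 200, 160, 128.

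**Spouses and supervisors.** The documents give no d or ICC for either group, so the employee values are borrowed as an assumption. Supervisors are taken at 200×.8=160, also an assumption.

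| Group and time | N | Power, d=.33, ICC .03 | Power, d=.30, ICC .01 | Detectable d at 80% power (ICC .01 to .03) |
|---|---|---|---|---|
| Spouses, no loss | 260 | .61 | .60 | .38 to .41 |
| Spouses, 4 months | 208 | .54 | .51 | .42 to .45 |
| Spouses, 9 months | 166 | .47 | .44 | .47 to .49 |
| Spouses, 9 months, 50% uptake | 128 | .39 | .36 | .53 to .55 |
| Supervisors, assumed 20% loss | 160 | .45 | .42 | .48 to .50 |

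The 9-month row uses the unrounded 166.4. The last column solves the formula for d at λ=2.93, the value that gives 80% power. For N=208 and ICC .01, for example, d = 2.93×√[4(.01+.99/8.667)/24] = .42.

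**Sensitivity.** With no clustering, λ = d√N/2. For all 260 spouses this is .33×√260/2=2.66 or .30×√260/2=2.42, with power .72 or .64. A one-sided test gives .65 to .67 at 208 and .57 to .60 at 166. A smaller, indirect effect on spouses of d=.20 with ICC .01 (an assumption) gives about .22 at 166.

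**The case against.** The strongest reply is that the sentence opens by referring to the preceding subsection, which states its limit to employees plainly, so the wording is loose and not false. That stands as far as it goes: the meaning can be recovered by reading both subsections. Even so, hypotheses listed as primary remain without any power or detectable effect.

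A reader might infer that the spouse retention figures contradict the 20%. They do not. The 20% is an employee assumption, and two populations may lose people at different rates. A reader might also blame the 36% loss for the low power. The table does not support that: 260 spouses with no loss reach only about .60. Power below .4 should not be given as the plan's own case either, because it needs 50% uptake. Compounding employee loss over two waves would be a further assumption, since the plan applies 20% once and names no time point.

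The spouse base may also be larger than 260. Recruitment Methods invites partners of participating employees and supervisors, whereas Number of Subjects counts employees' partners only. If supervisors' partners are included at the same 80% (an assumption), 700×.80=560, and 65% uptake gives 364, 291 and 233. Power is then .71 to .73 with no loss and .56 to .57 at 9 months, which is better but still below .80.

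Multiple imputation or full-information likelihood may recover some information, but would not be expected to take power beyond that of the full baseline group. Finally, nothing in the documents says that non-significant results will be read as no effect; that is a risk and not a stated plan.

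**Conclusion.** The point holds as an over-broad adequacy statement together with missing spouse and supervisor calculations. On the borrowed employee inputs, spouses have power of .51 to .54 at exactly the 20% loss that the sentence names, and .44 to .47 at the planned 9-month number. Supervisors have .42 to .45 under an assumed 20% loss. The precise values depend on the borrowed d and ICC and on two-sided testing. The shortfall from .80 does not depend on the ICC: for the planned 260 spouses it remains with no clustering and no loss.

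For employees, the stated .86 and .80 compute to .74 and .76, and the physical-health pair cannot come from one design at 500 and 400 people. Until those figures are recomputed, the adequacy sentence should not be kept even for employees.

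**What to change.** - **Power Analysis.** Recompute the four employee figures by one stated method, with sidedness given. Say that spouse and supervisor outcomes are not powered at d=.30 to .33. Give their detectable effects at 80% power, with the borrowed inputs labelled as assumptions: spouses about .42 to .45 (N=208), .47 to .49 (N=166) and .53 to .55 (N=128); supervisors about .48 to .50 (N=160, assumed).
- **Missing Data and the Application of Intent-to-Treat.** Limit the sentence to employee outcomes at 20% total loss, and attach the recomputed power.
- **Recruitment Methods and Number of Subjects.** Show spouse numbers across the 50-65% range: 200 to 260 at baseline, 160 to 208 at 4 months and 128 to 166 at 9 months, if only employees' partners count. Reconcile the two subsections on whether supervisors' partners are included, and adjust the numbers if they are.

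The cost is wording and a short recalculation, with no extra participants and no change to the design. The downside is that the stated figures become less favourable.
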